4.6. Benefit:Risk Assessment

Summaries of findings from both clinical and non-clinical studies conducted with CAB can be found in the Investigator's Brochure. The following section outlines the risk assessment and mitigation strategy for this protocol:

4.6.1. Risk Assessment

Potential Risk of Clinical Significance	Summary of Data/Rationale for Risk	Mitigation Strategy
Investigational Product (IP) GSK1265744/Cabotegravir		
Elevated liver transaminases	
A few subjects in the CAB program have experienced transaminitis (elevated liver transaminases characterised by predominant ALT elevation). Some of these subjects' transient transaminitis were explained by acute hepatitis C infection and others did not have alternative explanations, suggesting a mild form of Drug induced Liver Injury (DILI) without hepatic dysfunction which resolved upon withdrawal of treatment with CAB.
 
Cumulatively (through January 1, 2016) 1160 subjects have been exposed to oral CAB and/or IM CAB. Seventeen subjects have met protocol-defined liver stopping criteria, of which five are considered to represent possible or probable cases of DILI. Eight of the 17 subjects met liver stopping criteria after having received CAB IM, six subjects as a result of acute Hepatitis C, one acute HIV seroconversion and one possible or probable DILI following CAB IM or Placebo IM administration.
 
Of the five subjects with possible or probable cases of DILI, four subjects were receiving oral CAB and one subject developed probable DILI following CAB IM or Placebo IM administration. None of these subjects have developed evidence of hepatic dysfunction and all had improvements in AST and ALT over time upon withdrawal of CAB.
	
Exclusion criteria as described in Section 5.2 will prohibit subjects with current or chronic liver diseases and significant liver impairment based on screening liver chemistry including transaminases (ALT and AST).
 
A 4-week oral lead-in period is being implemented in this study, where all subjects will receive oral CAB prior to the administration of IM CAB to determine individual safety and tolerability
 
Liver transaminases (ALT and AST) will be closely monitored throughout this study (refer to Time & Events Table) and the liver chemistry stopping criteria will be adopted as described in Section 5.4.1 of this protocol. Subjects will be withdrawn from CAB treatment where no compelling alternative cause is identified. All instances of liver transaminase elevations will be followed to resolution. Subjects withdrawn from CAB treatment due to meeting liver chemistry stopping criteria will be regularly monitored both clinically and using liver chemistries to

Potential Risk of Clinical Significance	Summary of Data/Rationale for Risk	Mitigation Strategy
		determine progress towards resolution of the liver event
Injection Site Reactions (ISRs)	
Clinical, experience to date has demonstrated ISRs occur in the majority of exposed subjects treated with IM CAB but are generally mild (Grade 1) or moderate (Grade 2) and include events of pain, tenderness, erythema, or nodule formation of several days duration (median duration for individual events <1 week). ISRs may occur more than once in an individual subject receiving multiple injections. Although some Grade 3 ISRs were reported, overall ISRs have been well tolerated and have not to date been associated with an excess of subjects' withdrawal due to ISRs.
 
None of the ISRs was serious and no clinical significant complications were reported
	
Administration advice to minimize risk of poor administration technique giving rise to ISRs. Advice on care, monitoring, natural course, and treatment of ISRs given in study documentation
 
Advice to subjects on care of injection site on day/days immediately post administration, use of analgesia, compresses where appropriate.
 
Subjects will be closely monitored for ISRs particularly for signs of pain, tenderness, infections, erythema, swelling, induration, or nodules (granulomas or cysts) throughout the study. Complications of ISRs such as infections (abscess, cellulitis) and collections of fluid requiring drainage will be monitored
 
Significant ISRs may be photographed and referred to a dermatologist for specialist advice.

Potential Risk of Clinical Significance	Summary of Data/Rationale for Risk	Mitigation Strategy
Hypersensitivity Reactions (HSR)	
Hypersensitivity reactions have been reported with integrase inhibitors, including dolutegravir, and were characterized by rash, constitutional findings, and sometimes, organ dysfunction, including liver injury.
 
While there have been no clinical cases of hypersensitivity to CAB, there is a theoretical risk of systemic or severe hypersensitivity reactions with or without hepatic symptoms associated with use of IM CAB. The long exposures anticipated after IM CAB injection may complicate the management of a drug hypersensitivity reaction, were it to occur.
	
The risk of developing a hypersensitivity reaction post administration of IM CAB will be minimized by the use of a 4-week oral lead-in of CAB to determine individual safety and tolerability prior to the introduction of IM CAB.
 
Clinical assessments, laboratory tests (including liver transaminases) and vital signs will be performed throughout this study (refer to Time & Events Table). Results from these assessments may aid early detection of HSR.
 
Oral CAB will be withdrawn immediately for cases with suspected HSR during the lead-in phase. During oral and IM CAB treatment, any HSR reactions that occur would be managed supportively.

Drug-Drug Interactions (DDIs)	
Residual concentrations of CAB will remain in the systemic circulation of subjects for prolonged periods (months). Subjects discontinuing a LA regimen may be at risk for developing DDIs many weeks after discontinuing injectable therapy. Of note, in vitro and clinical evidence to date, indicates that with the exception of sensitive OAT substrates with narrow therapeutic index (e.g. methotrexate), CAB has a low risk for causing clinically significant drug interactions.
	
All subjects will be informed of prohibited medications throughout the study and updates provided as needed via informed consent.

Development of Resistance in the setting of HIV acquisition	
Residual concentrations of CAB LA would remain in the systemic circulation of participants for prolonged periods (up to 52 weeks in some subjects). Participants may be at risk for developing resistance to CAB many weeks after discontinuing injectable therapy were they to become newly infected with HIV.
	
All participants will be informed of this risk. Participants will be followed for 52 weeks from the time of the last injection with CAB. The risk of HIV acquisition should be minimized by

Potential Risk of Clinical Significance	Summary of Data/Rationale for Risk	Mitigation Strategy
		only including healthy volunteers at low risk for acquiring HIV, and by encouraging all subjects to practice safe sex for at least 52 weeks after the last injection of CAB LA. HIV testing will occur periodically throughout the study. If a participant acquires HIV on study he or she will be referred for appropriate care.
Inadvertent Intravenous Injection (Accidental Maladministration)	As with any intramuscular injection, it is possible that IM CAB can be inadvertently administered intravenously instead of intramuscularly resulting in higher than expected concentrations of CAB. This could be due to administrator error, improper injection technique and / or improper needle length used based on body type. The clinical consequences of overdose with CAB are currently unknown.	
All IM injections will be done under ultrasound guidance by a trained clinician, which will minimize the risk of intravenous administration.
 
Should IM maladministration be suspected at any time (e.g. suspected under or overdose or inadvertent IV dosing), a post dose ECG , vital signs or any other supportive testing may be obtained at the discretion of the investigator, and the medical monitor notified.
 
Laboratory samples for safety parameters will be closely monitored in all subjects. Additionally, 2 hour post dose PK samples will be obtained at a few early timepoints for determination of CAB concentration and possible pharmacokinetic correlation with safety parameters such as ECG changes.

Potential Risk of Clinical Significance	Summary of Data/Rationale for Risk	Mitigation Strategy
Study Procedures		
Anoscopy to obtain rectal fluid sampling	It is possible that the participant may experience mild discomfort, embarrassment or, rarely, pain (should they have another condition that is already causing pain in the area) during this procedure.	If there is any pain experienced during the procedures, the study clinician will adapt or stop the procedure.
Cervical and vaginal biopsy via speculum exam	It is possible that the participant may experience mild discomfort, embarrassment, or, rarely, pain during speculum exam and biopsies. There is also a small risk of bleeding and an extremely low risk of infection after biopsy. In rare circumstances, the bleeding may require blood transfusions and surgical repair. A small amount of discomfort during sexual intercourse may follow in the few days after the procedure.	If there is an adverse event, participants will be referred immediately to the appropriate care. If there is any pain experienced during the procedures, the study clinician will adapt or stop the procedures. Subjects should abstain from inserting anything into the vagina (e.g., tampons, sexual intercourse) within 72 hours after cervical or vaginal biopsies.
Colonic biopsies via flexible sigmoidoscopy	Flexible sigmoidoscopy is a commonly practiced medical procedure and the endoscopic procedures done in this trial will not involve any unusual risks or discomforts. The risks associated with these procedures include mild discomfort and the feeling of having a "bloated stomach". Endoscopic biopsies are painless and heal quickly within 3 days. On extremely rare occasions, the endoscopic procedure or biopsies may lead to pain, infection (sepsis), bleeding or perforation of the gastrointestinal tract. Perforation occurs approximately once out of every 10,000 procedures. If this extremely rare complication occurs, antibiotics and surgery to repair the tear may be necessary. In rare circumstances, the bleeding may require blood transfusions and surgical repair. Subjects will self-administer a 125 mL enema several hours prior to the flexible sigmoidoscopy procedure. The main risk from having an enema is temporary discomfort. Some air may be pumped into the rectum as well, causing a bloating or gassy sensation. Very rarely, the enema tip may cause a perforation, as described above. Subjects will also be asked to have nothing to eat for 8 hours prior to the endoscopy procedure.	This procedure will be performed exclusively by experienced practitioners of endoscopy, who are familiar with safety procedures and mitigation of any complications that should ensue.

Potential Risk of Clinical Significance	Summary of Data/Rationale for Risk	Mitigation Strategy
Phlebotomy for blood draws	There is a small risk of discomfort, bleeding, inadvertent arterial puncture, or adverse reaction with venipuncture such as fainting.	Should any bleeding occur, the procedure will be aborted at that puncture site and pressure will be held for the appropriate period of time. Should any adverse reactions to venipuncture occur, the participant will be referred immediately to the appropriate care.
Other		
Ultrasound guidance for IM injection	
There is no convincing evidence of adverse effects from ultrasound imaging, especially one-time, short-lived imaging which is expected to last less than a minute. No or minimal pain is associated with this procedure.
 
According to the World Federation of Ultrasound in Medicine and Biology Clinical Safety Statement for Diagnostic Ultrasound Imaging (http://www.wfumb.org/about/statements.aspx), "Diagnostic ultrasound has been widely used in clinical medicine for many years with no proven deleterious effects. However, investigations into the possibility of subtle or transient effects are still at an early stage. Biological effects (such as localized pulmonary capillary bleeding) have been reported in mammalian systems at diagnostically relevant exposures but the clinical significance of such effects is not yet known. Consequently, diagnostic ultrasound can only be considered safe if used prudently.
 
Ultrasound produces heating, pressure changes and mechanical disturbances in tissue. Diagnostic levels of ultrasound are capable of producing temperature rises that may be hazardous to sensitive organs and the embryo/fetus. Biological effects of non-thermal origin have been reported in animals but, to date, no such effects have been demonstrated in humans, except when a microbubble contrast agent is present.
	Ultrasound will be employed for the minimum time necessary in order to obtain the required visualization and will be performed by competent personnel who are trained and updated in safe procedural technique
MRI (non-enhanced) of injection site to visualize injection depot	FDA guidance on safety and use of Magnetic Resonance Imaging (http://www.fda.gov/Radiation-EmittingProducts/RadiationEmittingProductsandProcedures/MedicalImaging/ucm200086.htm) states: "MRI does not use ionizing radiation (high-energy radiation that can potentially cause damage to DNA, like the x-rays used CT scans). There are no known harmful side-effects associated with temporary exposure to the strong magnetic field used by MRI scanners. However, there are important safety concerns to consider before performing or undergoing an MRI scan:	All participants will be screened according to local hospital criteria and trial inclusion/exclusion before entering the MRI room to ensure they are able to have the MRI conducted to maximize the safety of this procedure.

Potential Risk of Clinical Significance	Summary of Data/Rationale for Risk	Mitigation Strategy
	
• The magnet may cause pacemakers, artificial limbs, and other implanted medical devices that contain metal to malfunction or heat up during the exam.• Any loose metal object may cause damage or injury if it gets pulled toward the magnet.• Dyes from tattoos or tattooed eyeliner can cause skin or eye irritation.• Medication patches can cause a skin burn.• The wire leads used to monitor an electrocardiogram (ECG) trace or respiration during a scan must be placed carefully to avoid causing a skin burn. Prolonged exposure to radio waves during the scan could lead to slight warming of the body."	

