2.2. Brief Background

CAB is an investigational HIV-1 INSTI that possesses attributes favorable for both HIV treatment and prevention indications. CAB has demonstrated potent *in vitro* activity against a broad range of HIV strains. Due to its unique physiochemical properties, CAB has been formulated as both a once daily oral tablet and a LA nanosuspension for monthly to quarterly intramuscular administration. The CAB tablet will serve as oral lead-in therapy to assess safety and tolerability prior to switching to the LA formulation for HIV-1 treatment and/or prevention. The LA-injectable, which has a plasma half-life of approximately 21-50 days, is a promising candidate for PrEP and has demonstrated protective antiviral activity in both rectal and vaginal non-human primate (NHP) Simian/Human Immunodeficiency Virus (SHIV)-challenge models [[Andrews, 2014](#); [Radzio, 2015](#)].

In a preclinical study, eight male rhesus macaques were injected with CAB LA (50 mg/kg IM) at two time points, 1 week prior to the first virus exposure and 4 weeks later [[Andrews, 2014](#)]. An additional eight male macaques were untreated and served as placebo controls. After weekly intrarectal challenges with SHIV162p3 [50 tissue culture infective dose (TCID)₅₀] for up to eight exposures, all eight placebo macaques became infected after a median of two rectal exposures (range 1 to 7). Of the eight CAB LA-treated macaques, none had detectable systemic viremia 10 weeks after the last virus challenge. In these protected animals, the plasma concentrations of CAB throughout the period of virus challenges were comparable to clinically relevant exposure in humans. In a similarly designed study, three intramuscular doses of CAB 50 mg/kg administered 4 weeks apart fully protected female pigtail macaques (n=6) from twice weekly low dose (50 TCID₅₀) SHIV162p3 challenges [[Radzio, 2015](#)]. These data support the continued development of CAB LA as a PrEP candidate for both men and women at high risk for HIV transmission.

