As of 01 January 2016, approximately 1160 adult subjects have been exposed to CAB in either oral or injectable formulations. Both healthy volunteers and HIV-infected patients have been dosed with oral CAB, and approximately 566 healthy volunteers and HIV-infected patients have received at least 1 injection of CAB LA. Previous Phase I and on-going Phase II studies have demonstrated that CAB is well tolerated when administered as both a once daily oral tablet and LA IM injection. The safety, tolerability, and

acceptability of CAB LA in HIV uninfected men is currently being evaluated in the ECLAIR study [GlaxoSmithKline Document Number [2013N184048_01](#)] and will be assessed in HIV uninfected men and women in the HPTN 077 Phase 2 study.

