The CAB population PK model has been updated with PK data from ÉCLAIR (an additional 94 males) and LATTE-2 (an additional 230 participants; 216 males and 14 females), significantly increasing the data in the population PK dataset. The absorption rate constant for the entire population following CAB LA for the new model was increased approximately 2-fold ($4.54 \times 10^{-4} \text{ hr}^{-1}$ to $9.19 \times 10^{-4} \text{ hr}^{-1}$; i.e., more rapid absorption) as compared to the previous model and resulted in higher peak to trough ratios than previously observed. Sex remains a significant covariate in the model affecting the absorption rate constant following LA administration (KA LA), reflecting slower absorption in females than in males. Additional data from HPTN077 will increase the data obtained from females in the model to improve understanding of the impact of sex on KA LA.

Simulations based on the updated population PK model have been conducted to evaluate several potential dosing regimens. Currently, the HPTN077 Cohort 2 regimen (CAB LA 600 mg IM at two time points 4 weeks apart and every 8 weeks (Q8W) thereafter) is planned for evaluation in long-term Phase 3 PrEP studies. CAB LA 600 mg IM is the largest CAB LA dose that can be administered by single injection (3mL of 200 mg/mL nanosuspension). For these reasons, a single 600 mg IM is the proposed dose for evaluation of plasma and tissue PK in this study. Simulated profiles following a single CAB LA 600 mg IM injection one week after discontinuation of the CAB 30 mg once daily oral lead-in to evaluate safety are shown for males and females separately (Figure 2, Figure 3). The profiles show the last oral dose, which are expected to achieve mean peak and trough concentrations of 7.5 $\mu\text{g/mL}$ and 4.2 $\mu\text{g/mL}$, respectively. Consistent with the impact of sex on absorption, males will achieve a higher C_{max} of ~3 $\mu\text{g/mL}$ than females, who will achieve a C_{max} of ~1.35 $\mu\text{g/mL}$. Plasma concentrations are expected to remain above 4x PA-IC₉₀ (0.664 $\mu\text{g/mL}$) for approximately 4 weeks and above PA-IC₉₀ (0.166 $\mu\text{g/mL}$) for approximately 8 weeks in 95% of males; greater variability in concentrations between 8 and 12 weeks post injection is expected in males. Plasma concentrations are expected to remain above the PA-IC₉₀ (0.166 $\mu\text{g/mL}$) in 95% of females throughout the 12-week tissue sampling period.

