7.1.2. CAB Injection, Compartmental PK Sampling, and Follow-up

Procedures	Day 1			Day 3	Day 5	Day 8	Week 4	Week 8	Week 12	Week 24	Week 36	Week 52	Withdrawal ¹
	Pre-dose ²	0h	4h	48h	96h	168h							
Interim Medical / Medication / Drug / Alcohol History	X												
Brief Physical Exam (Section 7.4.3)	X												X
Vital Signs (Section 7.4.4)	X			X	X	X	X	X	X	X	X	X	X
Pregnancy Test (Section 7.4.6)	X						X	X	X	X	X	X	X
Hematology with differential; Clinical Chemistry Tests (Section 7.4.6)	X						X	X	X				X
HIV Test (Section 7.4.6)									X	X	X	X	X
STD testing (Section 7.4.6)	X												
Administer CAB LA 600 mg IM		X											
Injection Site Reaction Assessment		X	X	X	X	X	X	X	X	X	X	X	X
AE Assessment ³	X	X	X	X	X	X	X	X	X	X	X	X	X
Concomitant Medication Review	X			X	X	X	X	X	X	X	X	X	X
Blood plasma PK Sampling	X		X	X	X	X	X	X	X	X	X	X	X
Luminal Fluid (CVF/RF) PK Sampling ⁴				X		X	X	X	X				
Tissue PK Sampling ⁴ (Table 4)				X ⁵		X	X	X ⁵	X				
MRI ⁶		X		X		X							

- Subjects who terminate before week 52 will be asked to return to the site for a withdrawal visit.
- On Day 1, study personnel must verify the following pre-dose assessments to be within normal limits prior to injection: brief physical exam, vital signs, pregnancy test (negative; FRP only), AE assessment, and concomitant medication assessment. If a clinical abnormality, clinically significant AE, or prohibited medication that precludes injection is observed/recorded, the medical monitor must be contacted for further instruction.
- AE assessment will include a brief, symptom-directed physical exam as needed.
- Female subjects may consent to have paired rectal tissue and rectal fluid samples collected at each time-point. Female subjects who do not wish to participate in rectal PK sampling may still participate in the study.
- Vaginal tissue will be collected only on Day 3 (48 hour) and Week 8.
- Non-contrast MR Imaging will be performed in a subset of up to 8 subjects (4 males and 4 females). The MRI at 0h will be performed immediately after CAB injection and before the 4h blood plasma PK assessment.

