7.4. Safety

Planned time points for all safety assessments are listed in the Time and Events Table (Section 7.1). Additional time points for safety tests such as vital signs, physical exams and laboratory safety tests may be added during the course of the study based on newly available data to ensure appropriate safety monitoring.

In order to monitor safety and to respond to occurrences of toxicity expeditiously, the team will hold conference calls on a regular basis during study implementation, and additional conferences calls will take place on an *ad hoc* basis. Study site investigators will be responsible for close monitoring and management of AEs, and will have detailed SOPs for the reporting of AEs and the management of toxicity. The Safety Monitor will be responsible for providing support to study investigators regarding the clinical management of individual participants (including decision-making surrounding eligibility, discontinuation/holds/termination of study drug, and clinical management).

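### Protocol 4.6.1 says ALT/AST are tested throughout the study, but 7.1.2 schedules no clinical chemistry for completers in the last 40 of 52 post-injection weeks

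*Protocol*

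**What the plan says.** Two rows of the risk table in Protocol 4.6.1 rely on continuing transaminase tests. The elevated-transaminases row says "Liver transaminases (ALT and AST) will be closely monitored throughout this study (refer to Time & Events Table". The hypersensitivity row says "laboratory tests (including liver transaminases) and vital signs will be performed throughout this study (refer to Time & Events Table". Both leave the timing to the Time and Events Table.

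For the injection phase that table is in 7.1.2. Its row "Hematology with differential; Clinical Chemistry Tests (Section 7.4.6" is marked at Day 1 pre-dose, Weeks 4, 8 and 12, and Withdrawal. It is blank at Weeks 24, 36 and 52. Table 5 (7.4.6) places ALT and AST in the clinical chemistry panel, and 7.1.2 has no separate liver panel. The Withdrawal column is for subjects who stop before Week 52. Section 4.1.3 describes Weeks 24 and 36 as visits for safety assessment and plasma PK.

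**The concern.** CAB LA is a single depot injection given to healthy volunteers and it cannot be withdrawn. Elevated transaminases are a named risk, and repeated ALT/AST testing is part of the stated mitigation. An investigator or ethics reviewer reading 4.6.1 would expect that testing to run to Week 52. Under 7.1.2 it stops at Week 12 for anyone who stays in the study. A subject who withdraws at Week 30 is scheduled for a panel, while one who completes Week 52 has none after Week 12.

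At stake is the chance to detect and follow a late ALT rise that causes no symptoms, and the laboratory evidence behind any safety statement about CAB LA beyond Week 12.

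**Working it through.** **Schedule.** The 7.1.2 rows have 13 visit columns. The vital signs, pregnancy, HIV and plasma PK rows were read against the same columns to confirm alignment. All four are marked at Weeks 24, 36 and 52, so the blanks in the chemistry row are not a table-reading artefact.

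**Interval without a scheduled test (completers).** 52 − 12 = 40 weeks; 40/52 = 76.9%. Scheduled post-injection panels: 3 (Weeks 4, 8, 12).

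| Late chemistry added | Longest interval without a test after Week 12 |
|---|---|
| none | 52 − 12 = 40 weeks |
| Week 24 only | 52 − 24 = 28 weeks |
| Weeks 24, 36 and 52 | 52 − 36 = 16 weeks |

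**Other provisions that might fill the gap.**
- 5.4.1 and Appendix 2 act once an ALT elevation is known.
- 7.4.6 repeats clinically significant abnormal values, so it needs a first test.
- 7.4 says that "laboratory safety tests may be added during the course of the study based on newly available data". This permits tests but schedules none.

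None of these gives a completer with no known abnormality an ALT/AST test after Week 12.

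**Expected yield.** Section 4.6.1 reports that "one subject developed probable DILI following CAB IM or Placebo IM administration". Section 2.2 gives approximately "566 healthy volunteers and HIV-infected patients have received at least 1 injection of CAB LA".
- Rate: 1/566 = 0.18%, exact (Clopper-Pearson) 95% CI 0.004% to 0.98%.
- In 16 injected subjects: 16 × 0.0018 ≈ 0.03 cases; at the upper limit 16 × 0.0098 ≈ 0.16.

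This covers any time after injection, not only after Week 12, and the one case may have received placebo.

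**Late exposure, illustrative only.** Inputs from the protocol: predicted LA Cmax about 3 µg/mL in males and 1.35 µg/mL in females (4.5); oral concentrations "expected to achieve mean peak and trough concentrations of 7.5" and 4.2 µg/mL respectively (4.5); and CAB LA "has a plasma half-life of approximately 21-50 days" (2.2). Assumptions: mono-exponential decline from Cmax, starting on the injection day or 7 days later, because tmax is not given.

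Level = Cmax × 0.5^((days − start)/half-life). Week 24 is day 168.
- Half-life 50 days: fraction 9.7% to 10.7%. Males: 0.29 to 0.32 µg/mL, which over 4.2 is 7.0% to 7.7% of the oral trough. Females: 0.13 to 0.14 µg/mL, 3.1% to 3.4%.
- Half-life 21 days: fraction 0.4% to 0.5%. Males: 0.3% to 0.4% of the oral trough.

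On these assumptions the Week 24 level in males is roughly 0.3% to 8% of the oral trough. With the 50-day half-life, males are at about 2.2% to 2.4% at Week 36 and 0.5% at Week 52.

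**The case against.** The strongest reply is that both risk-table rows defer to the Time and Events Table, and Sections 7 and 7.4 make that table the operative schedule. Sites therefore have one set of instructions, and the phrase in 4.6.1 is loose wording that an edit would cure. That is right about site conduct: a reader might infer that sites face conflicting orders, and they do not. It does not remove the mismatch, because the stated mitigation is broader than the schedule that is meant to deliver it.

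The 77% is a share of calendar time, not of risk. ALT is tested during the oral lead-in, when exposure is much higher, and ALT of 1.25 × ULN or more at Day 29 bars injection (5.4.1). A late result cannot change dosing after a single injection, and the protocol cites no late-onset signal. All of this stands and limits the importance of the point.

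A reader might also infer that the mitigation as a whole lapses after Week 12. The documents do not support that. The eligibility limits, the oral lead-in, and liver-event follow-up for 52 weeks or until resolution remain, as do adverse-event and vital-sign checks to Week 52. The hypersensitivity row loses less than the transaminase row, since it presents test results only as a possible aid to early detection.

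Finally, the exposure figures should not be read as upper bounds. They combine a typical predicted Cmax with an assumed decline, and individuals vary widely: Section 4.5 reports a between-subject CV of 139% for trough in an earlier 800 mg cohort. The 50-day case may equally be too high for a typical male. If the updated absorption constant of 9.19 × 10⁻⁴ per hour (4.5) governs the decline, the half-life is 0.693/0.000919 ≈ 754 hours, about 31 days, and Week 24 is near 2% of the oral trough.

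**Conclusion.** The inconsistency holds. The two rows of 4.6.1 state ALT/AST testing throughout the study, while 7.1.2 leaves completers without a scheduled test for the last 40 of 52 post-injection weeks. The missing element is routine late detection of a rise without symptoms, and nothing wider.

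The count follows directly from the schedule. The yield estimate, about 0.03 cases in 16 subjects (up to 0.16), assumes that the earlier program's rate applies here and that its one case received CAB. The exposure range is illustrative and depends on the assumed decline. No pharmacokinetic endpoint is affected. The point merits a correction because the mitigation is already stated, concerns healthy volunteers and is cheap to deliver; it is not evidence of a substantial unmonitored hazard.

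**What to change.** In 7.1.2, mark clinical chemistry at Weeks 24, 36 and 52, using the blood draws already made there for plasma PK and HIV testing. At minimum, mark it at one late visit; Week 24 has the highest remaining exposure of the three.

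The cost is about one tube and one panel per visit. At an assumed 5 to 10 mL each, three panels add 15 to 30 mL. Documented volumes are 12 PK samples × 4 mL + 6 mL for genetics = 54 mL. With assumed volumes for the other safety tubes, a completer's total is about 169 to 274 mL now and 184 to 304 mL with all three panels. This should fit the 500 mL cap in Section 7, but the site should confirm it against actual tube sizes.

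If the sponsor declines, limit the ALT/AST statements in both rows of 4.6.1 to testing through Week 12. That costs only a wording change and makes the risk table true, but it leaves late detection unscheduled.
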